3.4. Subject Selection

It is anticipated that approximately 30 subjects will be screened, with at least 20 eligible subjects enrolled in approximately 10 study centers across the United States.

[figure not shown]
3.4.1. Inclusion Criteria

To be eligible for study entry subjects must satisfy all of the following criteria:

- 1. Subjects ≥ 12 to < 17 years of age at the screening visit.
- Chronic AD for at least 2 years before the screening visit and confirmed according to the American Academy of Dermatology Consensus Criteria at the time of the screening visit.
- 3. Eczema Area and Severity Index (EASI) score ≥ 16 at both screening and baseline visits.
- 4. Investigator's Global Assessment (IGA) score ≥ 3 (based on the IGA scale ranging from 0 to 4, in which 3 is moderate and 4 is severe) at both screening and baseline visits.
- AD involvement ≥ 10% of Body Surface Area (BSA) at both screening and baseline visits.
- Peak (maximum) pruritus numeric rating scale (PP NRS) score of at least 4.0 at both screening and baseline visits:

7. Documented recent history (within 6 months before the screening visit) of inadequate response to topical medications (TCS with or without TCI).

- 8. Agree to apply a moisturizer throughout the study from the screening visit daily, and liberally as needed; agree to apply an authorized TCS from the screening visit and throughout the study as determined appropriate by the investigator.
- 9. Women of childbearing potential must agree either to be strictly abstinent throughout the study and for 12 weeks after the last study drug injection or to use an effective and approved method of contraception throughout the study and for 12 weeks after the last study drug injection. This criterion also applies to a prepubertal female subject who begins menses during the study.

Effective and approved methods of contraception applicable for the subject and/or their partner are defined below:

- Progestogen-only oral hormonal contraception
- Male or female condom
- Cap, diaphragm or sponge with spermicide
- Combination of male or female condom with cap, diaphragm or sponge with spermicide
- Combined (estrogen and progestogen containing-) oral, intravaginal, or transdermal hormonal contraception
- Injectable or implanted hormonal contraception
- Intrauterine devices
- 10. Subject and guardian willing and able to comply with all of the time commitments and procedural requirements of the clinical trial protocol, including daily diary recordings by the subject using an electronic handheld device provided for this study.
- 11. Understand and sign an Informed Consent Form (ICF) and Assent Form before any investigational procedures being performed.

3.4.2. Exclusion Criteria

Subjects will be excluded from the study if one or more of the following criterion are applicable:

- 1. Body weight < 30 kg.
- 2. Subjects meeting one or more of the following criteria at screening or baseline:
 - 2a. Had an asthma exacerbation requiring hospitalization in the preceding 12 months.
 - 2b. Reporting asthma that has been not well-controlled (ie, symptoms > 2 days per week, nighttime awakenings >1-3 times per week, or some interference with normal activities) during the preceding 3 months.
 - 2c. Asthma Control Test ≤ 19 (applies only for subjects with a history of asthma).

This document is confidential.

SAP Version: Final Version 3.0, 21-Sep-2020

Controlled Document ID: 3903A.01, Effective Date 29-Oct-2018

Filing requirements: TMF

- 2d. Peak expiratory flow < 80% of the predicted value.
- 3. Subjects with a current medical history of chronic obstructive pulmonary disease (COPD) and/or chronic bronchitis.
- 4. Cutaneous infection within 1 week before the screening visit or any infection requiring treatment with oral or parenteral antibiotics, antivirals, antiparasitics, or antifungals within 1 week before the screening visit. Subjects may be rescreened once the infection has resolved.
- 5. Requiring rescue therapy for AD during the run-in period, or expected to require rescue therapy within 2 weeks following the baseline visit.
- 6. Positive serology results for hepatitis B surface antigen [HBsAg] or hepatitis B core antibody [HBcAb], hepatitis C antibody, or human immunodeficiency virus [HIV] antibody at the screening visit:

Note: Subjects with a positive HBcAb and a negative HBsAg can be included in this clinical trial if hepatitis B surface antibody (HBsAb) is positive (considered immune after a natural infection).

- 7. Having received any of the treatments within the specified timeframe before the baseline visit as described in Protocol Section 8.3.3 (Table 3: Prior Treatments).
- 8. Subjects who failed to respond clinically to previous treatment with a biologic (eg, dupilumab) or a Janus kinase (JAK) inhibitor.
- 9. Pregnant women (positive serum pregnancy test result at the screening visit or positive urine pregnancy test at the baseline visit), breastfeeding women, or women planning a pregnancy during the clinical trial.
- 10. History of lymphoproliferative disease or history of malignancy of any organ system within the last 5 years, except for (1) basal cell carcinoma, actinic keratoses or squamous cell carcinoma in situ (Bowen's disease) that have been treated and have no evidence of recurrence in the last 52 weeks before the baseline visit, or (2) carcinoma in situ of the cervix.
- 11. History of hypersensitivity (including anaphylaxis) to an immunoglobulin product (plasma-derived or recombinant, eg, monoclonal antibody) or to any of the study drug excipients.
- 12. History of intolerance to low or mid potency TCS or for whom TCS is not advisable (eg, hypersensitivity to TCS, significant skin atrophy, etc.).
- 13. Known active or latent tuberculosis (TB) infection.
- 14. Known or suspected immunosuppression or unusually frequent, recurrent, severe, or prolonged infections as per investigator judgment.
- 15. History of or current confounding skin condition (eg, Netherton Syndrome, psoriasis, Cutaneous T-Cell Lymphoma [Mycosis Fungoides or Sezary Syndrome], contact dermatitis, chronic actinic dermatitis, dermatitis herpetiformis).
- 16. Any medical or psychological condition, or any clinically relevant laboratory abnormalities, such as but not limited to elevated ALT or AST (> 3 × ULN) in combination with elevated bilirubin (> 2 × ULN), at the screening visit that may put the subject at significant risk according to the investigator's judgment if he/she participates in the clinical trial, or may interfere with study assessments (eg, poor venous access or needle-phobia).
- 17. Planned or expected major surgical procedure during the clinical trial.
- 18. Subjects unwilling to refrain from using prohibited medications during the clinical trial.
- 19. Currently participating in any other clinical trial of a drug or device, participated in a clinical trial within the past 3 months before the screening visit, or is in an exclusion period (if verifiable) from a previous clinical trial.

3.5. Determination of Sample Size

Based on the variability of nemolizumab serum concentrations (observed in adults during previous studies), a sample size of 20 was considered sufficient to calculate PK parameters with adequate precision and to ensure adequate representation across the adolescent age range. No formal powering of the trial was performed to determine sample size requirement.

This document is confidential.

SAP Version: Final Version 3.0, 21-Sep-2020

Controlled Document ID: 3903A.01, Effective Date 29-Oct-2018

Filing requirements: TMF

It is anticipated that approximately 30 subjects will be screened, with at least 20 eligible subjects enrolled.

The study will attempt to enroll at least 3 subjects with low body weight (≤ 61 kg) for the interim analysis and approximately 6 total subjects with low body weight for the overall study population.

3.6. Treatment Assignment & Blinding

Eligible subjects will be sequentially assigned to receive treatment with open-label nemolizumab, based on the time of enrollment.

Although some subjects will be screened and assigned a subject identification number (SIN), they may not be eligible for enrollment/treatment, and thus they will not be enrolled in the study.

Dose modification of the study drug will not be permitted during the clinical trial.

Any inadvertent dose modification(s) should be reported to the sponsor/CRO.

In the event of a missed dose (ie, temporary discontinuation of the study drug), it will be documented in the case report form (CRF) that the drug has not been administered at the study visit, together with the reason (eg, for safety). Subjects will be asked to return to the study centers for all remaining visits and complete all study assessments and procedures.

3.7. Administration of Study Medication

Dosing frequency is scheduled for every 4 weeks, based on the baseline/Day 1 visit date. If a study visit occurs outside the visit window, study drug can be administered with a minimum of 3 weeks since the last injection. Future visits should be scheduled within the required windows based on the baseline/Day 1 visit date, while maintaining the minimum 3-week interval between 2 injections.

As described in Table 1, Nemolizumab (CD14152) will be administered as a subcutaneous injection, with a loading dose of 60 mg on Day 1, followed by injections of 30 mg every 4 weeks for 12 weeks.

Table 1 Dosing Scheme

Group	Dose on Day 1	Dose at Weeks 4, 8 and 12
1	60 mg	30 mg

3.8. Study Procedures

Subjects will be screened and complete a run-in period of at least 14 days before the baseline visit. Eligible subjects will enter a 16-week treatment period with nemolizumab 30 mg administered subcutaneously every 4 weeks, with a loading dose of 60 mg at baseline/Day 1.

The final dose of study drug will occur at Week 12 and subjects will complete the treatment period at the Week 16 visit. An 8-week follow-up period is scheduled (Week 24 visit) for subjects who do not immediately rollover (within 7 days following the Week 16 visit) into the nemolizumab open-label extension study. Subjects who prematurely discontinue the study before the Week 16 visit have to be followed for 12 weeks after their last dose of study drug.

The Schedule of Assessments is described in the protocol (Section 8.1.1).

4. Endpoints

4.1. Pharmacokinetic Endpoints

- Nemolizumab serum concentrations at Baseline, Weeks 1-2, 4, 8, 12, 16, 24 and Unscheduled visits for safety reasons.
- Nemolizumab serum PK parameters at steady state extrapolated with a population PK analysis (CI/F, V_d/F, T_{lag}, k_a, C_{max}, T_{max}, C_{trough}, AUC_{0-4w}, AUC_{0-8w}, AUC_{0-12w}, AUC_{0-16w}, AUC_{inf}, and t_{1/2}).

4.2. Immunogenicity Endpoints

 Anti-drug antibody (ADA) assessments (Screening, confirmatory, neutralizing antibody (NAb)), at Baseline, Weeks 4, 8, 16, 24 and Unscheduled visits for safety reasons.

4.3. Safety Endpoints

- Incidence of adverse events (AE), including treatment emergent adverse events (TEAEs),
 adverse events of special interest (AESIs) and serious adverse events (SAEs).
- Asthma Control Test (ACT): Screening, Baseline, Weeks 1-2, 4, 8, 12, 16, 24, and Unscheduled visits.
- Physical examination: Change from Baseline at all visits.
- Vital signs: Change from Baseline at all visits.
- Clinical laboratory values: Change from Baseline at Weeks 4, 8, 12, 16, 24 and Unscheduled visits for safety reasons.
- Spirometry (peak expiratory flow (PEF)): Change from Baseline at all visits.
- Electrocardiogram (ECG): Change from Screening at Week 16 and Unscheduled visits for safety reasons.

4.4. Secondary Endpoints

4.4.1. Pharmacokinetics

 Nemolizumab serum PK parameters calculated with a non-compartmental analysis (NCA): AUC_{0-4w}, AUC_{0-8w}, AUC_{0-12w}, and AUC_{0-16w}

4.4.2. Pharmacodynamics

- Blood biomarkers (eg, IL-31, TARC and/or other proteins) at baseline, Week 8, and Week 16
- Stratum corneum biomarkers (eg, IL-31 and/or other proteins) at baseline and Week 16 Biomarker analysis will be conducted by the designated CRO separately.

4.4.3. Efficacy

The following efficacy variables will be analyzed:

Absolute and percent change in EASI score from Baseline to Week 16.

Sponsor: Galderma Research & Development, LLC; Protocol No.: RD.06.SPR.116912, Version 6.0

- IGA success rate from Baseline to Week 16.
- Change in BSA involvement of AD, reported as a percentage of all major body sections combined.
- Absolute and percent change in weekly average of peak pruritus numeric rating scale (NRS) score from Baseline to Week 16.
- Absolute and percent change in weekly average pruritus NRS score from Baseline to Week 16.
- Absolute and percent change in weekly sleep disturbance NRS score from Baseline to Week 16.
- Percent change in SCORing Atopic Dermatitis (SCORAD) score from Baseline to Week 16.
- Number of topical AD medication-free days AD medication-free days.

4.4.4. Quality of life

 Dermatology Life Quality Index (DLQI) for subjects > 16 years of age or Children's Dermatology Life Quality Index (cDLQI) for subjects 12-16 years of age at Baseline and Week 16.

Page 16 of 59

Filing requirements: TMF

5. Analysis Populations

Three analysis populations will be used for this study: the Intent-to-Treat Population, the Safety Population and the Pharmacokinetic population.

5.1. Intent-to-Treat Population

The Intent-to-Treat (ITT) population will include all enrolled subjects who signed informed consent form. The ITT population will be used for all analyses of efficacy endpoints.

5.2. Safety Population

The Safety Population will include all subjects in the ITT who were administered at least one dose of study medication. Subjects will be analyzed according to the treatment actually received.

5.3. Pharmacokinetic Analysis Population

The Pharmacokinetic (PK) analysis population will include all subjects in the safety population who provide at least one post-baseline evaluable drug concentration value. PK endpoints will be analyzed using the PK population. Subjects will be analyzed according to the treatment actually received.

5.4. Protocol Deviations

Protocol deviations will be captured by the clinical monitoring team on an ongoing basis throughout the study. All protocol deviations related to study inclusion or exclusion criteria, conduct of the study, subject management, or subject assessments will be identified, evaluated, and resolved (if applicable) before the respective database lock (interim or final analysis). These deviations will be discussed in a case by case process and classified into major and minor deviations before the data base lock.

6. General Aspects for Statistical Analysis

6.1. General Methods

This section describes analytical analysis issues that relate to all or some of the analytic analysis sections that follow. It describes general guidelines for analysis as well as the following items:

- SAS version 9.4 or higher will be used.
- CCI will be responsible for reporting the demographic, safety, and efficacy data including listings of the administration information for collection of PK and PD samples.
- Unless otherwise specified, summaries will be presented by visit.
- The total number of subjects in the treatment group (N) will be used as the denominator for percentage calculations, unless stated otherwise in the table shell.
- Continuous variables will be summarized using the number of observations (n), mean, standard deviation (SD), median, minimum, and maximum. Categorical variables will be summarized using number of observations (n) and percentages of subjects.
- Subject data listings will be presented with the ITT population for efficacy assessments, with the Safety Population for safety assessments and with the PK population for PK assessments, unless stated otherwise.
- In general, the listings will be sorted by subject number, and assessment date (and time) if applicable.
- Multiple assessments at a given time point (repeat, and unscheduled) will not be included in summary tables unless specified otherwise, but will be included in the listings.

6.2. Key Definitions

The date of first treatment is defined as the date of first injection of nemoluzimab.

The date of last treatment is defined as the date of last injection of nemoluzimab.

Study day is defined as the number of days from the date of first treatment and will be calculated as follows:

- If the event date≥date of first treatment, study day = event date–date of first treatment+1.

 Treatment Day 1 is therefore defined as the day of first treatment.
- If the event date<date of first treatment, study day = event date-date of first treatment.

The baseline value will be taken as latest value prior to first injection of nemoluzimab. For subject enrolled but not treated, the baseline value will be the latest value prior to the treatment assignment.

A subject's date of last participation in the trial is the last date of contact and is recorded as the date of completion or date of withdrawal on the completion page of the CRF.

Treatment period is defined as the period between the date of first treatment.

- Up to the date of Week 16 for subjects who completed the treatment period
- Up to the earliest date between 4 weeks after the last study drug injection or the date of early termination for subjects discontinued the treatment period.

6.3. Missing Data

The primary method to impute the missing values for the efficacy assessments will be as follows:

Continuous Endpoints: To impute the missing values for efficacy continuous endpoints, Last Observation Carried Forward (LOCF) approach will be used. Only post-baseline visits will be imputed. Screening or Baseline information will not be used for LOCF. As sensitivity analysis, observed case (OC) will be conducted.

Binary Endpoints: All missing values will be treated as a Non-Responder for the binary endpoints. LOCF and OC will be used to impute the missing values as sensitivity analysis.

LOCF and Non-Responder will be performed to all subsequent, scheduled, missing post-baseline assessments. And when impute the missing data using LOCF and Non-Responder, all efficacy data after use the rescue therapy will be considered as missing. There will be no imputations for missing PK and Safety parameters. Imputation rules for missing dates in AEs and medications are described in the corresponding sections.

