### Phototherapy

Whenever possible, investigators should first use topical medication as rescue therapy, before escalating to systemic therapies. If subjects receive topical treatments or phototherapy as rescue therapy, study drug administration should be continued unless there is a safety concern according to the investigator's judgment. If subjects receive systemic rescue therapy, the study drug administration must be permanently discontinued.

For the purpose of efficacy analysis, subjects receiving any rescue therapies will be considered as treatment failures.

Further, the use of any rescue therapies should be documented in the CRF.

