# 9.3 Imputation of Missing Data

The primary method to impute the missing values for the efficacy assessments will be as follows:

Continuous Endpoints: To impute the missing values for efficacy continuous endpoints, Last Observation Carried Forward (LOCF) approach will be used. In addition, Observed Case (OC) will be carried out as sensitivity analysis.

**Binary Endpoints:** All missing values will be treated as a Non-Responder for the binary endpoints. LOCF and OC will be used as sensitivity analysis to impute the missing values.

Use of Rescue Therapy: All Efficacy Data, Except OC, Will Be Set To Missing After Rescue Medication Is Used. In OC Analysis, No Observed Data After Subject Has Received Rescue Treatment Will Be Excluded.

There will be no imputations for PK, missing laboratory, and vital sign data. Further details on imputation of missing data will be provided in the SAP.

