All medications (prior and concomitant medications, rescue medications, and background TCS) will be listed on the ITT population.

8. Efficacy

All the efficacy analyses will be based on the ITT population. All efficacy variables will be summarized by visit from baseline unless specified otherwise. For efficacy analysis, unscheduled visit or ET visit data will be considered for by-visit summary.

All efficacy analysis will be performed using LOCF or Non-responder imputation (unless stated otherwise) and also performed with observed cases (OC) as sensitivity analysis (see Section 6.3 for more details). LOCF and Non-responder will be performed at all post-baseline visits up to Week 24.

In LOCF or Non-responder analyses, all efficacy data will be set to missing after rescue medication is used. In OC analyses, all data will be included even if subject has received rescue medication.

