8.2. Investigator Global Assessment

The Investigator Global Assessment (IGA) is a 5-point scale (defined in Table 3) used by the investigator to evaluate the global severity of AD and the clinical response.

Table 3: IGA 5-point scale

Status	Score	Definition	
Clear	0	Minor, residual hypopigmentation/hyperpigmentation, no erythema or induration/papulation, no oozing/crusting.	
Almost clear	1	Trace faint pink erythema, with barely perceptible induration/papulation and no oozing/crusting.	
Mild	2	Faint pink erythema with mild induration/papulation and no oozing/crusting.	
Moderate	3	Pink-red erythema with moderate induration/papulation with or without oozing/crusting.	
Severe	4	Deep or bright red erythema with severe induration/papulation with oozing/crusting.	

IGA score and change from baseline will be summarized by visit using LOCF and OC.

IGA success is defined as 0 (clear) or 1 (almost clear) and at least 2 grade improvement change from baseline. The IGA treatment success rate will be obtained as the ratio between the number of subjects achieving IGA treatment success and the number of subjects with available IGA result at the visit, and will also be summarized by visit from baseline using Non-Responder, LOCF and OC.

Proportion of subjects achieving IGA success using Non-Responder will be displayed graphically.

For the LOCF analysis, the imputation will be performed based on the recorded IGA per visit, and the imputed IGA treatment success rate will be based on the imputed values.

All IGA data will be listed.

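### LOCF without baseline drops subjects rescued or lost early from continuous efficacy tables labelled ITT, and the IGA LOCF run carries a pre-rescue success past rescue

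*SAP*

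**What the plan says.** - **Continuous endpoints.** Protocol section 9.3 makes LOCF the primary method: "To impute the missing values for efficacy continuous endpoints, Last Observation Carried Forward (LOCF) approach will be used". It does not say whether baseline may be carried, and it leaves further detail to the SAP. SAP section 6.3 supplies that detail: "Screening or Baseline information will not be used for LOCF".
- **Data after rescue.** SAP section 8: "In LOCF or Non-responder analyses, all efficacy data will be set to missing after rescue medication is used". Protocol section 9.3 has the same rule. Both documents keep post-rescue values in the observed-case (OC) analysis.
- **Status of rescued subjects.** Protocol section 7.5.8.1.2: "For the purpose of efficacy analysis, subjects receiving any rescue therapies will be considered as treatment failures". This is not limited to binary endpoints, and no value is given for a continuous score.
- **Population.** SAP section 5.1: "The ITT population will be used for all analyses of efficacy endpoints". ITT means all enrolled subjects who gave consent, and SAP section 6.2 defines a baseline even for someone enrolled but never treated.
- **IGA success.** The primary analysis counts missing as non-response. LOCF and OC are sensitivity analyses. For the LOCF run, SAP section 8.2 says "the imputed IGA treatment success rate will be based on the imputed values".

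**The concern.** Taken together, these rules leave a subject with no usable post-baseline value without an entry at any post-baseline visit in the continuous LOCF tables. The same subject, if rescued early, is a failure in the primary IGA table and simply absent from the EASI, BSA, SCORAD and NRS tables, although all of them carry the ITT label. When the missing subject is an early rescue, the mean that remains is likely to look better than it should.

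The IGA LOCF run has a different problem. A subject who met the success definition and was then rescued keeps the success at later visits. LOCF runs to Week 24 while the last dose is at Week 12, so a subject successful at Week 16 and rescued during follow-up would be shown as a Week 24 success.

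**Working it through.** The plan states no efficacy power, effect size or rescue rate. The sample of 20 rests on PK precision, with no formal powering, so there is no plan figure to reproduce. The check traces the rules and then sizes them under stated assumptions.

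**When does a subject have nothing to carry?**

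- *Clinic scores.* The first post-baseline visit is Day 10 ± 3, that is Days 7 to 13 (protocol section 7.2). Rescue or loss before it leaves no scheduled value. If that visit is missed, the limit moves to the Week 4 visit, Day 29 ± 3, that is Days 26 to 32. An unscheduled or early termination visit before rescue would supply a value, because SAP section 6.6 windows those visits.
- *Diary scores.* The first window is Days 3 to 9 and needs at least 4 daily scores (SAP sections 6.6 and 8.5). Rescue on Day 5 leaves at most Days 3, 4 and 5, which is 3 scores, so no Week 1-2 value exists. Rescue on Day 6 leaves 4 scores if the same-day score counts and 3 if it does not. From Day 7 on, 4 or more are possible.

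**Effect on a mean change.** Let k of 20 subjects have no usable value and let the others average m (assumed). The LOCF table shows m on n = 20 - k. With the k subjects at zero change, the mean is m × (20 - k)/20.

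| Assumed m | k = 1 (n = 19) | k = 2 (n = 18) | k = 3 (n = 17) |
|---|---|---|---|
| -40% | -38.0% | -36.0% | -34.0% |
| -60% | -57.0% | -54.0% | -51.0% |
| -70% | -66.5% | -63.0% | -59.5% |

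Each subject therefore shifts the mean by 40/20 = 2.0 to 70/20 = 3.5 points.

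**How likely is at least one?** With an assumed per-subject risk p, the chance among 20 is 1 - (1 - p)^20. This gives 18% at p = 1%, 33% at 2%, 64% at 5% and 88% at 10%.

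**IGA LOCF run.** One carried success out of 20 is 1/20 = 5 percentage points at that visit.

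**The case against.** The strongest reply is that the SAP only follows the protocol. Protocol section 9.3 itself blanks efficacy data after rescue, applies LOCF to continuous endpoints, and names LOCF as a sensitivity method for binary ones. It hands the remaining imputation detail to the SAP. This stands. A reader might infer that the baseline bar is an undeclared change, since SAP section 14 foresees none. The documents do not support that: filling a gap the protocol delegated is not a departure. Nor is this mainly a conflict between SAP and protocol. The tension lies inside the protocol, between sections 7.5.8.1.2 and 9.3, and the SAP inherits it.

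The case is also narrow, and this stands too. Exclusion criterion 5 removes subjects expected to need rescue within 2 weeks of baseline, and rescue in that period is discouraged, though not forbidden. Early termination visits include EASI, IGA, BSA and SCORAD, so a dropout who attends one without prior rescue has clinic values to carry. OC tables exist for all the affected scores. Each summary reports n, so a shortfall is visible.

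Forcing non-success after rescue makes the IGA LOCF run agree with the primary analysis for rescued subjects. That is true, but LOCF would still differ for data missing for other reasons.

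Finally, zero change for subjects without post-baseline data does not deal with someone rescued after one improved visit, whose improvement is still carried. That is correct, and it needs its own sentence in the plan.

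**Conclusion.** The point holds as a minor one. The stated rules can leave an ITT subject out of every continuous LOCF table, and can show a rescued subject as an IGA success in a sensitivity run. Neither result fits the protocol's treatment-failure statement.

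The size is about 2.0 to 3.5 points of mean EASI change per affected subject, or 0 to 7 points for 0 to 2 subjects. Both the mean of -40% to -70% and the count are assumptions; the documents give neither.

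A reader might infer that the excluded subjects are always the worst outcomes, so that the bias always favours the drug. The documents support that expectation only for early rescue. Subjects may also leave for reasons unrelated to efficacy, such as consent withdrawal, and for them the direction is unknown.

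No main conclusion depends on this. Efficacy is secondary, single-arm and descriptive, the interim decision concerns PK and safety, and primary IGA success is protected by non-responder imputation.

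**What to change.** 1. In SAP section 6.3, state that an ITT subject with a baseline but no usable post-baseline value is included with baseline carried (zero change), at least as a sensitivity analysis beside the current LOCF table. Report the number of such subjects and the reasons by visit.
2. In SAP section 8.2, state that in the IGA LOCF run a rescued subject is a non-success from rescue onward. Keep LOCF for other missing data.
3. State how treatment failure applies to continuous endpoints for a subject rescued after a usable visit, so that protocol sections 7.5.8.1.2 and 9.3 can be read together. If the last pre-rescue value is to be kept, say so and say that the failure rule then governs binary endpoints only.

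The cost is a few SAP sentences and, if the sensitivity route is chosen, one more summary per continuous endpoint. No new data are needed. Some secondary figures may be slightly less favourable.
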